3.2.2 Secondary Endpoints

The following secondary endpoints are related to the safety of immunosuppression withdrawal.

- The proportion of subjects who have graft loss or who die after initiation of immunosuppression withdrawal.
- The time from the start of immunosuppression withdrawal to
 - the first episode of acute rejection requiring treatment,
 - the second episode of acute rejection not requiring treatment, or
 - the diagnosis of chronic rejection.
- The distribution of histologic severity among rejection episodes.
- The incidence of adverse events.
- Changes in renal function, blood pressure, cholesterol level, and glucose control.

Other secondary endpoints include

- Immunosuppression-free duration, defined as the time from discontinuation of immunosuppression to end of trial participation or to time of restarting immunosuppression;
- Results of mechanistic studies and clinical assessments at various time points that allow for the definition of profiles associated with tolerance;
- Results of mechanistic studies and clinical assessments that allow for definition of profiles associated with liver allograft rejection.

3.3 Stratification Variables

Selected analyses will present data grouped by clinical phenotypes of tolerant and not-tolerant. A subject is defined to be tolerant if s/he is successfully withdrawn from immunosuppression for at least one year. The definition of tolerant corresponds to the primary endpoint.

3.4 Overall Study Design and Plan

This is a prospective multicenter, open-label, single-arm trial in which 20 pediatric recipients of parental living-donor liver allografts will undergo gradual withdrawal of immunosuppression with the goal of complete withdrawal. Subjects on stable immunosuppression regimens with good organ function and no evidence of acute or chronic rejection or other forms of allograft dysfunction will be enrolled. Subjects will undergo gradual withdrawal of immunosuppression and will be followed for a minimum of 4 years after completion of immunosuppression withdrawal. Immunologic and genetic profiles will be collected at multiple time points and compared between tolerant and nontolerant subjects.

3.5 Study Population

Subjects will be selected from those pediatric recipients of parental living related donor hepatic allografts with adequate and stable graft function and no evidence of rejection or

significant allograft dysfunction. Subjects must meet all of the inclusion criteria and none of the exclusion criteria outlined in the following section.

3.5.1 Inclusion and Exclusion Criteria

Inclusion Criteria

- Living-donor liver transplantation from a parental donor.
- Age less than 18 years at the time of transplantation.
- At least 4 years since transplantation.
- Availability and willingness of parental liver donor to participate in the trial.
- Liver biopsy at screening demonstrating no evidence of acute or chronic rejection and a less than stage 2 fibrosis on the Ishak scale.
- Negative urine pregnancy test at entry and agreement to use a medically acceptable form of birth control during the study for women of childbearing potential.
- Negative purified protein derivative (PPD) test results or history of appropriate treatment.

Exclusion Criteria

- Indication for transplantation liver failure due to autoimmune disease, such as autoimmune hepatitis, primary sclerosing cholangitis, or primary biliary cirrhosis.
- Hepatitis B infection as defined by the presence of HBSAg or active treatment for hepatitis B.
- Hepatitis C infection as defined by the presence of antibody against hepatitis C.
- Serologic evidence of autoimmunity defined as abnormal antinuclear, anti-smooth-muscle, antimitochondrial, or anti-liver-kidney microsomal antibody titers greater than or equal to 1:160.
- Transplantation of a second organ before, simultaneously, or after liver transplantation; or liver retransplantation.
- Aspartate or alanine aminotransferase (AST or ALT) greater than 2 times the upper limit of normal.
- Total bilirubin and direct bilirubin, and either alkaline phosphatase or gamma-glutamyl transferase (GGT) greater than 2 times the upper limit of normal.
- Clinically significant change in hepatic function in the past 26 weeks.
- Glomerular filtration rate (GFR) less than 40 mL/min/1.73 m².
- Immunosuppression with
 - 50% dose increase in a current agent within 26 weeks of screening, or
 - more than one agent within 52 weeks of screening.
- Any systemic illness requiring or likely to require immunosuppressive drug use.
- Human immunodeficiency virus (HIV) infection.
- Pregnancy or breastfeeding.
- Unwillingness or inability to comply with study requirements and procedures.

3.6 Treatment Regimens

The subjects in this study will be gradually withdrawn from immunosuppression with the goal of complete withdrawal. The algorithm for immunosuppression withdrawal is shown in Figure 1. For tacrolimus, high dose is defined as ≥ 0.08 mg/kg/day; low dose is < 0.08 mg/kg/day. For cyclosporine, high dose is defined as ≥ 3 mg/kg/day; low dose is < 3 mg/kg/day.

During the withdrawal process (see Figure 1), additional monitoring at the current immunosuppression dose level may be done before continuing on to the next scheduled dose reduction. In such instances, gradual withdrawal must resume, or a biopsy must be performed, within 4 weeks of the previously scheduled dose reduction.

Figure 1. Immunosuppression withdrawal. (*See protocol section 5.1 for definition of *high dose* and *low dose*.)

3.7 Sample Size Determination

A total of 20 subjects will be enrolled in the study. There are no published data available with respect to the success of immunosuppression withdrawal exclusively in living-donor pediatric liver transplant subjects 4 years or more post transplant. The sample size of 20 is thus based on clinical experience and judgment in order to provide a broad, initial pilot estimate of the proportion of subjects meeting the primary endpoint in this subject population for which no prior data exist. For example, if 9 of 20 subjects are successfully withdrawn from immunosuppression, the point estimate of the success proportion is 45% (95% CI: 23.1%, 68.5%, based on the exact binomial method). If 4 of 20 are successfully tapered, the point estimate is 20% (95% CI: 5.7%, 43.7%). This broad, initial estimate can subsequently serve in the design of future immunosuppression withdrawal studies in this subject population.

4. GENERAL ANALYSIS AND REPORTING CONVENTIONS

The following analyses and reporting conventions will be used:

- Categorical variables will be summarized using counts (n) and percentages (%) and will be presented in the form n (%). Percentages will be rounded to 1 decimal place.
- In general, in frequency tables of variables with different categories (e.g., for discontinuation reason, race): if no subjects belong to a certain category, including Missing, across all treatment groups, then the printing of this category should be suppressed. Otherwise, if the number of subjects in a category for a treatment group is zero, then a zero should be displayed for the number, and the percentage should be left blank.
- Numeric variables will be summarized using n, mean, standard deviation (SD), median, min, max. The min/max will be reported at same level of significance as original data. The mean and median will be reported at 1 more significant digit than the precision of the data and SD will be reported at 2 more significant digits than the precision of the data. Descriptive statistics will be displayed in the order: n, mean, SD, median, min, max

- Following SAS default rules, the median will be reported as the average of the two middle numbers if the dataset contains even numbers.
- Test statistics including t and z test statistics will be reported to two decimal places.
- P -values will be reported to 3 decimal places if greater than 0.001. If less than 0.001 than report '<0.001'. A p -value can be reported as 1.000 only if it is exactly 1.000 without rounding. A p -value can be reported as 0.000 only if it is exactly 0.000 without rounding.
- All statistical calculations will be performed using the SAS System version 9.1 (or higher).
- Tables and listings will be generated as RTF files with Courier New font, size 8. Figures will be generated as CGM files. Separate stacked files will be created for the tables, listings, and figures and converted to PDF prior to delivery.
- The program name, creation date, and data extraction date will be included in the footer of all displays (For example, Program: *Program Name* Creation Date: HH:MM/DDMMMYYYY Data Extraction Date: DDMMMYYYY)
- In general, columns with character values will have the header and column values left aligned. Numeric columns will be centered around their decimal place with headers also centered.
- In the first column, if text wraps onto another line indent 1 additional space. For subgroups, indent 2 spaces.
- Units of measurement - International units SI will be used for clinical laboratory data as a standard presentation. The metric system will be used whenever possible. Thus, weight will be in kilograms and height in centimeters. Temperature will be presented in Celsius degrees.
- For general footnotes, 'Note:' will come before any bracketed footnotes.
- All listings will be sorted in order of treatment, subject, and time of assessment (e.g., visit, time, and/or event).
- Episodes of rejection will be determined by the diagnoses from the central pathologist. All references to rejection episodes in this Statistical Analysis Plan refer to central pathology reads.

If departures from these general conventions are present in the specific evaluations section of this SAP then those conventions will take precedence over these general conventions.

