#### **3.3.2 Secondary Endpoints**

##### **3.3.2.1 Safety of Immunosuppression Withdrawal**

1. The proportion of participants who have graft loss or who die after initiation of immunosuppression withdrawal.
2. The time from the start of immunosuppression withdrawal to
  - a. the first episode of acute rejection requiring treatment,
  - b. the second episode of acute rejection not requiring treatment, or
  - c. the diagnosis of chronic rejection.
3. The distribution of histologic severity among rejection episodes.
4. The incidence of adverse events.
5. Changes in renal function, blood pressure, cholesterol level, and glucose control.

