### 5.5.2 Diagnosis, Grading, and Monitoring of Rejection

Allograft biopsy will be used to diagnose and grade rejection. Biopsies will be read locally for clinical decision-making, according to the Banff global assessment criteria. The liver biopsy will then be reviewed centrally at the ITN Liver Pathology Core Laboratory at which time protocol grading will be determined. If the biopsy does not demonstrate rejection, an evaluation for other causes of liver dysfunction will be performed. A diagnosis of rejection will necessitate monitoring of LFTs according to clinical standards. Changes in LFTs will be evaluated as follows:

- **If normal or below normal at baseline:**
  - *Substantially improved* when the value is less than or equal to the upper limit of normal.
  - *Improved* when the value is less than 1.5 times the upper limit of normal.
  - *Not improved* when the value is greater than or equal to 1.5 times the upper limit of normal.
- **If above normal at baseline:**
  - *Substantially improved* when the value is less than or equal to 1.2 times baseline.
  - *Improved* when the value is less than 1.5 times baseline.
  - *Not improved* when the value is greater than or equal to 1.5 times baseline.

An episode of rejection is deemed resolved when LFTs are substantially improved per definitions provided.

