### **5.5.4 Treatment of Chronic Rejection**

A diagnosis of chronic rejection is indicated when a biopsy fulfills the Banff criteria and total and direct bilirubin are above normal. Chronic rejection will be treated per the standard of care.

Participants who experience chronic rejection will be considered to have failed immunosuppression withdrawal (see section 5.3).

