### 6.5.2 Tissue Handling and Disposition During Rejection Episodes

Biopsies to rule out rejection will be handled similarly, except that 1 cm in saline will be sent in formalin to the local pathology laboratory for analysis instead of to the protocol chair. Any extra tissue beyond 4 cm, however, will be placed in RPMI with 20% fetal calf serum and sent to the protocol chair for intrahepatic lymphocyte studies.

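### Time to rejection counts only centrally read episodes and drops the treatment terms of the declared endpoint, so a rejection diagnosed and treated at the site but centrally negative has no event.

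*SAP*

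**What the plan says.** **Source of a rejection episode.** SAP section 4 says "Episodes of rejection will be determined by the diagnoses from the central pathologist" and adds that "All references to rejection episodes in this Statistical Analysis Plan refer to central pathology reads". It lets a specific section override the general conventions, but SAP 9.2.2(2), 9.3.2(2) and 10.4.2 contain no override.

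**Who reads what.** Protocol 5.5.2 says "Biopsies will be read locally for clinical decision-making, according to the Banff global assessment criteria", and continues: "The liver biopsy will then be reviewed centrally at the ITN Liver Pathology Core Laboratory at which time protocol grading will be determined". Under Protocol 5.3.2 and 5.5.3.3, any rejection requiring treatment ends withdrawal and counts as failure.

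**Tissue.** At screening, Protocol 6.5.1 has both laboratories work from one block. After screening, the formalin centimetre goes whole to the core laboratory. For a biopsy to rule out rejection, Protocol 6.5.2 adds a separate local piece: "1 cm in saline will be sent in formalin to the local pathology laboratory for analysis instead of to the protocol chair".

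**Endpoint declared and endpoint analysed.** Protocol 3.3.2.1 and SAP 3.2.2 declare time to "the first episode of acute rejection requiring treatment", to the second acute episode not requiring treatment, or to chronic rejection. Protocol 9.2.2.1 and SAP 9.2.2(2) and 9.3.2(2) analyse time to the first acute episode or first chronic rejection diagnosis, with no treatment condition.

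**Chronic rejection.** Protocol 5.5.4: "A diagnosis of chronic rejection is indicated when a biopsy fulfills the Banff criteria and total and direct bilirubin are above normal".

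**The concern.** The declared endpoint depends partly on treatment, and treatment is decided at the site on the local read. The analysis filters every episode through the central read. Suppose a site diagnoses rejection in a child, treats it and stops withdrawal, and the core laboratory's separate piece shows no rejection. That child has had the outcome the endpoint describes, yet contributes no event to the time-to-rejection curve and no episode to the severity table. Because the two laboratories examine different tissue, the negative central read does not show that the local read was wrong.

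The analysed endpoint departs from the declared one in two opposite ways. It is narrower, because a treated but centrally negative episode is excluded. It is broader, because a single mild, untreated, centrally positive episode counts, although Protocol 5.5.3.2 allows withdrawal to resume after such an episode resolves. No section says what to do when the two reads disagree, and no sensitivity analysis is planned. At stake is a safety estimate from 20 participants, where one episode is visible in the result.

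**Working it through.** **1. One discordant case traced through the plan** (site diagnoses and treats rejection; central read negative)

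| Output | Is the case captured? |
|---|---|
| Primary endpoint (SAP 9.2.1) | Yes, as a failure: back on immunosuppression |
| Disposition reasons (SAP 6.1) | Yes, as treated rejection, though section 4 taken literally makes the category ambiguous |
| Adverse event tables (SAP 10.3) | Yes, if recorded as an adverse event |
| Dysfunction listing (SAP 10.4.4) | Yes, with final clinical diagnosis and treatment |
| Time to rejection (SAP 9.2.2(2), 9.3.2(2)) | No event |
| Severity table (SAP 10.4.2) | No row: the denominator is rejection episodes |

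**2. What happens to that child's follow-up time.** SAP 9.1.1 gives a Kaplan-Meier censoring rule but names only time off immunosuppression. Nothing states how time to rejection is censored when drug is restarted without a counted event. Protocol 5.3.2 keeps such a child in follow-up for 52 weeks after liver tests improve. Unless a rule is added, that period may enter the curve as rejection-free time while the child is on immunosuppression.

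**3. The plan's own figures.** The exact binomial intervals in SAP 3.7 reproduce: 9/20 gives 23.1% to 68.5%, and 4/20 gives 5.7% to 43.7%. They are not in dispute.

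**4. Size.** Inputs: N = 20 (SAP 3.7); acute rejection in 14% to 43% of earlier cohorts (Protocol 1.2.3.4). Then 0.14 × 20 = 2.8 and 0.43 × 20 = 8.6, or about 3 to 9 participants. Assumptions: each has one locally diagnosed, treated rejection, and each is centrally negative independently with probability d. The documents give no value for d, so a range is shown.

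Expected events lost = R × d. Chance of losing at least one = 1 − (1 − d)^R.

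| Treated rejections R | d = 5% | d = 10% | d = 20% | d = 30% |
|---|---|---|---|---|
| 3 | 14% | 27% | 49% | 66% |
| 7 | 30% | 52% | 79% | 92% |
| 9 | 37% | 61% | 87% | 96% |

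At d = 10%: 1 − 0.9³ = 0.271 and 1 − 0.9⁹ = 0.613. Expected losses are 3 × 0.10 = 0.3 and 9 × 0.10 = 0.9 events. Over the whole range they run from 3 × 0.05 = 0.15 to 9 × 0.30 = 2.7. Each lost event is 1/20, or 5 percentage points of the cohort.

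**5. Does the median change?** With no earlier censoring, the curve for 20 participants reaches 0.5 only with 10 or more events. If all 11 failures in the 9/20 example were treated rejections, losing 2 would take events from 11/20 (55%) to 9/20 (45%), and the median from reached to not reached. At 9 events, the top of the documents' range, the curve ends at 1 − 9/20 = 0.55. The median is then not reached even with no discordance.

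**The case against.** **Central grading is the protocol's own rule.** Protocol 5.5.2 assigns protocol grading to the central laboratory, and SAP section 4 follows it. In an open-label, single-arm trial there is good reason to keep unblinded site judgement out of the endpoint. This stands: the central-only analysis is legitimate and should stay. It does not supply a rule for discordant reads or restore the treatment terms of the declared endpoint.

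**The episodes are not lost to the reader.** A reader might infer that treated rejections disappear from the safety record. The documents do not support that, as the first table shows. The gap is confined to the time-to-rejection estimate and the severity distribution.

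**The direction is not fixed.** A reader might infer that harm is necessarily understated. Central reads can also add episodes, from for-cause biopsies or from the scheduled biopsies in Protocol 6.5, and dropping the treatment condition adds mild untreated ones. This stands.

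**The median flip is a chosen scenario.** It needs 11 of 20 treated rejections, against about 3 to 9 from the documents, and Protocol 5.3.1 and 5.3.2 provide for failure without rejection. This stands, and the conclusion does not use it.

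**Chronic rejection.** A reader might infer that the SAP drops the bilirubin condition. It does not say so: section 4 speaks of episodes, while 9.2.2(2) speaks separately of a chronic rejection diagnosis. This is an ambiguity to close; an outright contradiction is not shown.

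**Conclusion.** The point holds for time to rejection and the severity table, and leaves the primary endpoint untouched. As written, the plan analyses a different endpoint from the one it declares, and it gives no event to a rejection that was diagnosed and treated at the site but is centrally negative. With 3 to 9 treated rejections and an assumed 10% discordance, the chance of losing at least one event is 27% to 61%; over 5% to 30% discordance it is 14% to 96%. These figures rest on an assumed discordance rate, independent reads, and every historical rejection being treated. They measure losses only, and the net error could go either way. The documents do not support the stronger conclusions that the central read is the wrong source, that harm is certainly understated, or that the median would change. This is a cheap improvement.

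**What to change.** - **SAP 9.2.2(2) and 9.3.2(2):** add a Kaplan-Meier analysis of the endpoint declared in SAP 3.2.2. Its events are the first acute rejection diagnosed and treated at the site whatever the central read, the second untreated acute episode, or chronic rejection. Date each event at the diagnosing biopsy, whether for-cause or scheduled, and name the read that identifies untreated episodes. Keep the central-only analysis beside it.
- **SAP 10.4.2:** keep the central grade for severity and add a local/central agreement count. Give its denominator, since Protocol 6.5.1 assigns no local piece for scheduled biopsies after screening.
- **SAP 9.1.1:** state how time to rejection is censored when immunosuppression is restarted without a counted event.
- **Chronic rejection:** state that the SAP uses the Protocol 5.5.4 definition, or reconcile the two.

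Cost: SAP wording, one extra analysis row and one small table. SAP 10.4.4 already calls for final clinical diagnosis, biopsy dates and treatment, so little or no new data collection should be needed. The downside is that unblinded site treatment decisions enter the added row, and the reported rejection rate may be slightly higher. No clinical rule changes.

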5. ANALYSIS POPULATIONS

Intent to treat (ITT) sample will be defined as all subjects who have signed informed consent and are enrolled. For the purpose of these analyses enrollment is defined as beginning the screening process for participation in the study.

Per protocol (PP) samples will be defined as all subjects in whom immunosuppression withdrawal is attempted.

- Per protocol 1 (PP1) sample will be defined as all subjects in whom immunosuppression withdrawal is attempted.
- Per protocol 2 (PP2) sample will be defined as all subjects without inclusion/exclusion criteria protocol deviations in whom immunosuppression withdrawal is attempted.

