### **3.2 ASSENT AND CONSENT FOR PARTICIPATION**

Consent must be obtained from individuals eligible for screening assessments before any screening assessments are performed to determine their eligibility for trial participation. Participants who meet the eligibility criteria (defined in sections 4.2 and 4.3) and have continued willingness to participate will then be enrolled in the study.

Requirements for the assent and informed consent process will depend on the participant's age:

**4–6 years** A parent or legal guardian will sign the consent form for the participant.

**7–12 years** The participant will sign the assent form and a parent or legal guardian will sign the consent form.

**13–17 years** The participant and a parent or legal guardian will both sign the consent form.

**≥18 years** Only the participant will be required to sign the consent form.

Informed consent for blood drawing must also be obtained from the parent who was the liver donor and will be requested from the parent who is not the donor.

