### 3.6 PACE OF ENROLLMENT AND STUDY DURATION

Enrollment is defined as starting on the day that immunosuppression withdrawal is initiated. Enrollment is planned for 2 years and will be limited to a maximum of two participants every 4 weeks. Maximum patient participation is up to 11 years; therefore, the total study duration is projected to be a maximum of 13 years.

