## **9.5 RANDOMIZATION, STRATIFICATION, AND BLINDING**

Individuals who are deemed qualified for the study will be enrolled and assigned a unique participant number within each site. All clinical activities performed in conjunction with this study will be performed in an unblinded manner. However, mechanistic assays will be performed in a blinded fashion because group assignments of tolerant or nontolerant individuals will be unknown until the completion or failure of immunosuppressive withdrawal. Given that this is a one-arm study, there will be no randomization procedure performed.

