6.1 Disposition of Subjects

The disposition of enrolled subjects throughout the study will be listed and summarized in tables.

The numbers and percentages of subjects enrolled, completed, discontinued from immunosuppression withdrawal, terminated from protocol, in each analysis population, as well as reasons for terminating the protocol early will be presented. For subjects discontinuing immunosuppression withdrawal early, the reasons for discontinuing withdrawal early will also be presented. Analysis populations will be derived according to the definitions in Section 5.

Reasons for terminating the study early include:

- ‘Voluntary Withdrawal’
- ‘Death’
- ‘Lost to Follow Up’
- ‘Adverse Event’
- ‘Protocol Deviation’

- ‘Other’

Reasons for discontinuing study medication/treatment early include:

- ‘Protocol Deviation’
- ‘Voluntary Discontinuation from Weaning’
- ‘Terminated from Study’
- ‘Second episode of mild rejection not requiring treatment’
- ‘Any episode of Rejection (mild, moderate, or severe) requiring treatment’
- ‘Chronic rejection’
- ‘Requirement for use of corticosteroid bolus therapy’
- ‘Abnormal LFTs in the absence of biopsy-proven rejection that do not substantially improve within maximum interval’
- ‘Other’

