9.2.2 Secondary Efficacy Variables

1) Immunosuppression-free duration: a continuous variable measured in days and is defined as: date of end of trial participation or date of restarting immunosuppression – date of completing withdrawal. All subjects completing withdrawal at any time will be included.

2) Time to Rejection: time from initiation of immunosuppression withdrawal to first episode of acute rejection or first diagnosis of chronic rejection measured in days and defined as date of first episode of acute rejection or date of first diagnosis of chronic rejection – date of

initiation of immunosuppression withdrawal. All subjects initiating withdrawal (PP1 sample) will be included.

3) Graft Loss or Death:

Proportion of subjects who have graft loss or who die after initiation of immunosuppression withdrawal: a continuous variable taking on values between 0 and 1, the numerator is the total number of subjects who experience either graft loss or death after initiation of immunosuppression withdrawal and the denominator is the total number of subjects initiating immunosuppression withdrawal (PP1 sample). This analysis will also be done on the PP2 sample.

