9.3 Analysis Methods

Analysis methods for clinical end points, described in detail below, are summarized in Table 9-1.

Table 9-1 Table of Efficacy Variables and Analysis Methods

Endpoint (section reference)	Analysis Technique (section reference)	Analysis Sample
Primary		
Proportion of subjects who are successfully withdrawn from immunosuppression ‡	Proportion with exact 95% confidence interval	PP1, PP2
Secondary		
1) Immunosuppression-free duration	Median Time and 95% CI	All subjects completing withdrawal
2) Time to Rejection	Median Time and 95% CI	PP1
3) Graft Loss or Death	Proportion with exact 95% confidence interval	PP1, PP2

‡ Defined as those who remain off immunosuppression for at least 1 year.

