9.3.2 Secondary Efficacy Analyses

- 1) Median immunosuppression-free duration will be estimated for all subjects completing withdrawal. Duration will be displayed graphically with a Kaplan-Meier curve and the corresponding median and two-sided 95% confidence interval.
- 2) Median time from initiation of immunosuppression withdrawal to first episode of acute rejection or to first diagnosis of chronic rejection will be estimated for the PP1 sample. Duration will be displayed graphically with a Kaplan-Meier curve and the corresponding median and two-sided 95% confidence interval.
- 3) The proportion of subjects experiencing graft loss or death after initiation of immunosuppression withdrawal will be descriptively summarized for the PP1 and PP2 samples as well as the ITT sample with 95% confidence intervals using an exact binomial method.

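### Run on the SAP's screening-based ITT sample, the supplementary graft-loss-or-death row counts subjects who cannot have an event; the SAP should fix one denominator (minor)

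*SAP*

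**What the plan says.** **When enrollment starts.** SAP Section 5 defines the ITT sample as consented, enrolled subjects and adds: "For the purpose of these analyses enrollment is defined as beginning the screening process for participation in the study". SAP 6.1 makes that binding for programming: "Analysis populations will be derived according to the definitions in Section 5".

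The supplied protocol dates it later. Section 3.6 (and the synopsis) says: "Enrollment is defined as starting on the day that immunosuppression withdrawal is initiated". Section 3.2 says that those who meet the eligibility criteria and "have continued willingness to participate will then be enrolled in the study". Section 9.5 says: "Individuals who are deemed qualified for the study will be enrolled and assigned a unique participant number within each site". These three are not identical, but none puts enrollment at the start of screening.

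**Which samples are used for graft loss or death.**
- Protocol 9.2.2.1 asks for this endpoint in the PP and ITT samples.
- SAP 9.3.2(3) has it "descriptively summarized for the PP1 and PP2 samples as well as the ITT sample with 95% confidence intervals".
- SAP 9.2.2(3) counts only events after withdrawal has begun, and "the denominator is the total number of subjects initiating immunosuppression withdrawal (PP1 sample"), with a repeat on PP2. It does not mention ITT.
- In SAP Table 9-1, the row "3) Graft Loss or Death" lists PP1 and PP2 only.

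**The concern.** The endpoint counts only events that follow the start of withdrawal, so the natural denominator is the set of subjects who started it. Under SAP Section 5 the ITT sample can be larger. Protocol 3.2 requires consent before any screening assessment, and the screening biopsy at visit −1 helps decide eligibility (Protocol 4.2 and 6.1). A subject who consents and then fails screening is therefore in the SAP's ITT sample without ever being exposed.

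The SAP does not settle whether the ITT row uses that larger set or keeps the denominator of 9.2.2(3). If it uses the larger set, the error runs one way only: the proportion and its upper confidence limit both shrink. What is at stake is one reported line on the trial's most serious safety outcome, which would look more reassuring than the experience of the subjects actually withdrawn.

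**Working it through.** **Inputs**
- Planned number starting withdrawal: 20 (Protocol synopsis and 3.1). SAP 3.7 also says 20 will be enrolled, which agrees with 20 withdrawals only if enrollment has the protocol's meaning or nobody fails screening.
- Interval: two-sided 95%, exact binomial (SAP 3.7 and 9.3.2(3)).
- Number consented and screened but never withdrawn, *s*: not given in either document. The values below are assumptions.

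**Formula.** For *x* events in *n* subjects, the Clopper-Pearson limits are
- lower = Beta quantile at 0.025 with parameters (*x*, *n* − *x* + 1), or 0 if *x* = 0;
- upper = Beta quantile at 0.975 with parameters (*x* + 1, *n* − *x*).

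With *x* = 0 the upper limit is 1 − 0.025^(1/*n*).

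**Reproducing the plan's own figures.** 9/20 gives 45% (23.1% to 68.5%), and 4/20 gives 20% (5.7% to 43.7%). Both match Protocol 9.3 and SAP 3.7.

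**Effect of the denominator.** A subject who never starts withdrawal adds 1 to the denominator and can add nothing to the numerator, so the proportion is multiplied by 20/(20 + *s*): 20/25 = 0.80 for *s* = 5, and 20/30 = 0.67 for *s* = 10.

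| Assumed *s* | *n* | 0 events: upper limit | 1 event: rate (upper limit) | 2 events: rate (upper limit) |
|---|---|---|---|---|
| 0 (same as PP1) | 20 | 16.8% | 5.0% (24.9%) | 10.0% (31.7%) |
| 5 | 25 | 13.7% | 4.0% (20.4%) | 8.0% (26.0%) |
| 10 | 30 | 11.6% | 3.3% (17.2%) | 6.7% (22.1%) |

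Zero-event check: 1 − 0.025^(1/20) = 16.8%; 1 − 0.025^(1/25) = 13.7%; 1 − 0.025^(1/30) = 11.6%. At the small end, a single never-withdrawn subject gives 1 − 0.025^(1/21) = 16.1%, a shift of 0.7 points. With *s* = 0 there is no effect.

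With zero events the point estimate is 0% whatever the denominator, so only the upper limit moves.

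**The case against.** The strongest reply is that little depends on this row, and most of that reply stands.

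- **The ITT row is not an SAP invention.** Protocol 9.2.2.1 asks for it. The row is legitimate; under Protocol 3.6 its denominator would be essentially the withdrawn set. The incomplete places are SAP 9.2.2(3) and Table 9-1.
- **The dilution is conditional.** SAP 9.2.2(3) already gives the correct denominator, and a careful programmer might apply it to every sample. What is established is an inconsistency; the diluted rate follows only if 9.3.2(3) is read together with Section 5, as SAP 6.1 directs.
- **The true rate stays visible.** The PP1 and PP2 rates appear in the same item. SAP 10.1 makes PP1 and PP2 the default for safety, SAP 6.1 reports population sizes, and deaths and graft losses have their own displays (SAP 10.4.1 and 10.4.3). Under Protocol 3.5.2 any death or graft loss triggers suspension whatever the rate, and no hypothesis test is attached.
- **Version lag may explain the mismatch.** SAP 13 cites protocol version 4.0, and SAP 3.4 gives a minimum follow-up of 4 years where the supplied protocol gives 8.

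What does not yield is the conflict inside the SAP. Sections 9.2.2(3), 9.3.2(3) and Table 9-1 disagree about the samples whichever protocol version applies, and one permitted reading gives a denominator that does not fit the endpoint.

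**Conclusion.** The point holds as a minor one. As written, the SAP allows an ITT proportion for graft loss or death whose denominator includes subjects who were never at risk of the event as defined. If 5 to 10 such subjects are assumed on top of 20 withdrawn, the zero-event upper limit is understated by 3.1 to 5.2 points (16.8 − 13.7 and 16.8 − 11.6), and a single event reads as 4.0% or 3.3% instead of 5.0%. The size rests wholly on that assumed number and on 20 subjects starting withdrawal. It is confined to one supplementary descriptive row.

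Three stronger readings are tempting, and the documents do not support them:
- *The trial's graft-loss-or-death result is biased.* The PP1 and PP2 results are unaffected and are reported beside the ITT row.
- *The primary success proportion is diluted as well.* SAP 9.3.1 and Table 9-1 analyse it in PP1 and PP2 only. Protocol 9.2.1 does ask for an ITT analysis, but its absence from the SAP is a separate matter and lends no weight here.
- *The SAP altered the protocol's enrollment definition.* Version 4.0 is not among the documents, so it can be said only that the SAP does not match the supplied protocol.

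**What to change.** 1. In SAP 9.2.2(3), 9.3.2(3) and Table 9-1, state that the denominator for graft loss or death is the subjects who started withdrawal, in every sample reported, and make the three places list the same samples. Protocol 9.2.2.1 supports keeping ITT in that list.
2. In SAP Section 5, align the enrollment definition used for ITT outcome analyses with Protocol 3.6, or record the difference and its reason in SAP 14.
3. Screened subjects can still be shown in the disposition and baseline displays. No rebuilding of populations across the SAP is needed.

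The cost is wording only: no new data, no change in sample size and no change in conduct. Two consequences should be accepted openly. The ITT upper limit becomes less favourable (for example 16.8% instead of 13.7% with no events and 5 assumed never-withdrawn subjects), and the ITT row then essentially repeats PP1.
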